Subjects who meet the criteria for clinically meaningful progression of SSc-ILD (see Section 6.5.5) during the Double-blind Treatment Period or Follow-up Period should have a change in background therapy. Subjects taking less than the maximal specified dose of mycophenolate (3 g/day MMF or 2160 mg/day MPS) can have the mycophenolate dose increased while IMP is continued. Subjects taking the maximal specified dose of mycophenolate who have clinically meaningful progression should have the IMP discontinued and be treated according to the local standard of care. If a nonbiologic immunosuppressant (such as cyclophosphamide [oral or intravenous]) is initiated, then mycophenolate must be discontinued.

If a subject discontinues IMP, then the subject should complete the early termination visit and then the remaining scheduled visits. At a minimum, the subject is expected to complete the trial visits at Weeks 12, 24, 36, 52, 64, 76, 88, and 104, as well as the Safety Follow-up period Week 12 visit. Subjects with discontinued IMP can come to the other scheduled visits during the trial period according to the Investigator's judgment.

Subjects who withdraw from the treatment period would have an early termination visit followed by entrance into the Safety Follow-up Period.

Subjects who withdraw from the trial (eg, withdraw consent, lost to follow-up, or death; see Section 5.5.2) would not have any additional trial visits.

Regardless of treatment completion or not, all subjects will be followed up by the site for survival from the subject's last visit on the trial until death or end of the trial. Subjects who have clinically meaningful progression of SSc other than ILD should be treated according to the local standard of care.

[figure not shown]
During the Double-blind Treatment Period, efficacy assessments will include evaluations of pulmonary function (forced vital capacity [FVC] and DLCO), HRCT, and PRO questionnaires. Routine safety, HRQoL, CCI, and PK assessments will be performed as described in the Schedule of Assessments (Table 1 and Table 2).

CCI

The trial design is displayed in Figure 1.

Figure 1 Trial Design

IV = intravenous; EOT = end of trial; pts = patients; Q4 weeks = every 4 weeks; SSc-ILD = systemic sclerosis-associated interstitial lung disease.

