7.3 Efficacy Assessments

Efficacy assessments include evaluation of lung function (FVC and DLCO) and lung abnormalities on HRCT. Assessments will be performed as described in Table 1 and Table 2.

Relative change is defined as percentage change from baseline FVC percent predicted (eg, change from FVC 80% predicted to FVC 70% predicted corresponds to an absolute change of 10% and a relative change of 12.5%).

In this trial, full volume HRCT of the chest will be performed at Sponsor-qualified imaging centers per guidelines outlined in an imaging manual. High resolution computer tomography will be performed on all trial subjects during the Screening Period and at Months 6, 12, and 24 (Weeks 24, 52, and 104; or early termination, if applicable). To ensure comparability, the same scan, equipment, method, and technique used during the baseline HRCT scan should be used for all the subsequent HRCT scans. For all subjects, HRCT scans will be performed with no contrast agent administration, reconstructed every 0.6 to 2 mm, using a low-dose protocol.

The HRCT images will be analyzed by computer-based quantitative scoring system and also by visual review by a central imaging review panel. The HRCT analysis will focus on changes visual and CAD scores for lobar lung fibrosis evaluation. Changes in the lung fibrosis scores from the Screening Period HRCT will be used to evaluate the treatment responses.

Detailed imaging procedures of HRCT will be defined in a separate imaging manual, and detailed image analysis procedures of HRCT will be defined in an imaging review charter.

Radiation Dose

The radiation dose that results from the entire scan can be described as having a whole body effective dose of 2.1 milliSieverts (mSv). Thus, for the 4 scans given over the 104 weeks (2 years) in this trial, the estimated total body effective dose would be 8.4 mSv. The average annual exposure from natural sources of radiation in the USA, for example, is approximately 3.0 mSv per year, and a radiation worker (such as a radiologic technologist or a radiologist) is allowed 50 mSv per year, for a total of 6.0 and 100 mSv, respectively, over 2 years. Therefore, this trial delivers the equivalent of approximately 1.4 times the expected natural radiation exposure and 8.4% of what a radiation worker is allowed over a 2-year period. This is considered acceptable, given the potential utility of the derived data.

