8.5 Description of Statistical Analyses

8.5.1 General Considerations

An outline of key statistical analyses is provided below. Full details of planned analyses will be provided in the Statistical Analysis Plan, to be finalized and approved prior to the interim futility analysis.

It is the intention of this trial that all subjects will adhere to the same visit schedule regardless of whether they have discontinued IMP prematurely. In addition, subjects who discontinue early from IMP will undergo an early termination visit to perform the same assessments scheduled for the Week 104 visit.

Multiple Comparisons/Multiplicity

During the primary analysis, hypothesis testing of the primary endpoint and key secondary endpoints will be formally performed for the abituzumab 1500 mg versus placebo under the family-wise Type I error rate following a hierarchical testing procedure to control for multiplicity. For these endpoints, statistical significance will be met at one-sided $p < 0.025$ and the corresponding two-sided 95% confidence intervals will be provided. CCI [REDACTED]

CCI [REDACTED]

Subgroups

The primary and key secondary endpoints and key safety data will be analyzed by subgroup. The subgroups of interest will be prespecified in the Statistical Analysis Plan, including the stratification factors of baseline FVC % predicted ($< 70\%$ versus $\geq 70\%$) and duration of prior mycophenolate use (< 6 months versus ≥ 6 months).

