8.5.3 Analysis of Secondary Endpoints

Analysis of Key Secondary Efficacy Endpoints

The key secondary endpoints will be tested for abituzumab 1500 mg versus placebo, using data for subjects on trial treatment, in the following order after the primary endpoint is met.

1. The Mahler TDI at Week 52 will be analyzed using a mixed-effects model adjusting for baseline FVC% predicted, duration of prior mycophenolate use at baseline, and Mahler BDI.
2. The absolute change in SGRQ total score at Week 52 will be analyzed using a mixed-effects model adjusting for baseline FVC% predicted, duration of prior mycophenolate use at baseline, and baseline SGRQ score.
3. The absolute change from baseline in mRSS at Week 52 in subjects with dcSSc at baseline will be analyzed using a mixed-effects model adjusting for baseline FVC% predicted, duration of prior mycophenolate use at baseline, and baseline mRSS.
4. The absolute change from baseline in QLF in the region of highest severity at Week 52 will be analyzed using an ANCOVA model adjusting for baseline FVC% predicted, duration of prior mycophenolate use at baseline, and baseline QLF.
5. Overall survival will be analyzed using a stratified log-rank test and presented by Kaplan-Meier estimates and 95% confidence interval, including the survival data available up to the analysis cut-off date. A Cox proportional hazards regression model will be used to obtain hazard ratios and 95% confidence intervals adjusting for baseline FVC% predicted and duration of prior mycophenolate use at baseline.

The mixed-effects model will include random intercept, treatment, and visit as fixed effect terms, treatment-by-visit as the interaction term, adjusting for baseline covariates. An unstructured covariance matrix will be used as the default option. Missing data is assumed MAR.

Missing data for binary endpoint will be imputed as non-responders.

Analysis of Other Secondary Efficacy Endpoints

CCI [REDACTED]

[REDACTED]

[REDACTED]

Analysis of Safety Endpoints

Adverse events will be summarized by treatment group, by severity, and by relationship to IMP. Serious AEs, AEs leading to treatment discontinuation, and AESI will be summarized by treatment group.

Summary statistics will be used to present changes from baseline in continuous laboratory and vital sign data. Shift tables will be used to present changes in categorical laboratory parameters. Figures may be generated to assist safety evaluation.

Analysis of Quality of Life Endpoints

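### QLF alone among the continuous key secondary endpoints gets a single-visit Week 52 ANCOVA, which leaves the scheduled Week 24 scan unused and has no visible missing-data rule

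*Protocol*

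**What the plan says.** Protocol 8.5.3, item 4, says that QLF change at Week 52 "will be analyzed using an ANCOVA model adjusting for baseline FVC% predicted"; the other covariates are duration of prior mycophenolate use and baseline QLF. Items 1 to 3 (TDI, SGRQ, mRSS) use a mixed-effects model with treatment, visit and their interaction. The paragraph describing that model adds "Missing data is assumed MAR". No reason is given for treating QLF differently. The rules that are visible elsewhere cover other endpoints: worst-outcome carry-forward for FVC% predicted (8.5.2) and non-responder imputation for binary endpoints (8.5.3).

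Protocol 7.3 schedules HRCT at screening and "at Months 6, 12, and 24 (Weeks 24, 52, and 104; or early termination, if applicable"; Table 1 agrees. After stopping IMP, "At a minimum, the subject is expected to complete the trial visits at Weeks 12, 24, 36, 52, 64, 76, 88, and 104". Also, "subjects who discontinue early from IMP will undergo an early termination visit to perform the same assessments scheduled for the Week 104 visit", and Table 2 includes HRCT at that visit. However, "Subjects who withdraw from the treatment period would have an early termination visit followed by entrance into the Safety Follow-up Period", and subjects who withdraw from the trial have no further visits. Anyone in these last two groups who leaves before Week 52 has no Week 52 scan by design.

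On which data count, 8.5.3 says the key secondary tests are run "using data for subjects on trial treatment". Protocol 8.5.2 says the primary and other efficacy endpoints use everything collected, whatever the adherence or rescue use.

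Protocol 8.5.1 leaves full detail to the Study SAP. Only the Final Analysis addendum was supplied.

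**The concern.** A single-visit ANCOVA is fitted, by default, to subjects with an outcome at that visit. A subject with a Week 24 scan but no Week 52 scan then contributes nothing. There are two consequences:

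- **Precision.** The Week 24 scan carries information about the missing Week 52 value, and it is not used.
- **Assumption.** The estimate is unbiased in general only if missingness at Week 52 is unrelated to QLF change, given treatment and the baseline covariates. The model used for the other three endpoints also allows missingness to depend on earlier observed visits.

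The second matters if subjects whose fibrosis has worsened by Week 24 are more often missing at Week 52. Under an effective drug there are more such subjects on placebo, so the completer comparison loses more poor outcomes there and the difference shrinks. Protocol 5.2.5 says QLF change can precede FVC change. FVC-based progression at the maximal mycophenolate dose leads to IMP discontinuation (6.5.5). Under an on-treatment reading of 8.5.3, those subjects' Week 52 scans would be left out even if they attended.

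**Working it through.** **Inputs.** 175 subjects at 2:2:1 give 175 × 2/5 = 70 per compared arm (Protocol 5.1). The test is one-sided at 0.025 (8.5.1). The plan gives no QLF figure to reproduce. The only planning values are for FVC: 150 mL, SD 300 mL (8.1). With these, n = 2 × (1.960 + 0.842)² × (300/150)² = 62.8, so 63 per arm for 80% power; 63/0.90 = 70, and 70 × 2.5 = 175. That fits 80% power with 10% dropout, but the stated power and dropout are blacked out, so it confirms nothing. It only makes 10% a reasonable first scenario. Everything below about QLF is assumed.

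**Precision.** Let n24 and n52 be the numbers per arm with each scan, and ρ the correlation between the two changes given baseline.

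- Completers only: Var = σ²/n52.
- With Week 24, monotone missingness: Var = σ²[(1 − ρ²)/n52 + ρ²/n24].
- Ratio = 1 − ρ²(1 − n52/n24).

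At 10% missing with Week 24 available in all, n52 = 63, n24 = 70 and the ratio is 1 − 0.1ρ².

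- ρ = 0.6: √0.964 = 0.982, an SE 1.8% smaller.
- ρ = 0.8: √0.936 = 0.967, an SE 3.3% smaller.

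If only half of those missing Week 52 have a Week 24 scan, n24 = 66.5. The gain falls to about 1.0% (√0.981) and 1.7% (√0.966).

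Power for an assumed 0.5 SD effect, 70 per arm, ρ 0.5 to 0.9, and half to all of those missing having a Week 24 scan:

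| Missing at Week 52 | Completers: power (n per arm) | With Week 24: power (effective n) |
|---|---|---|
| 10% | 80.1% (63) | 80.6–83.3% (64–69) |
| 20% | 75.4% (56) | 76.5–82.4% (58–67) |
| 30% | 69.7% (49) | 71.6–81.2% (51–65) |

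**Attenuation when dropout depends on Week 24.** Simulated with a true Week 52 effect of 0.5 SD, a Week 24 effect of 0.25 to 0.4 SD, ρ 0.6 to 0.8, and one dropout rule for both arms whose log-odds rise by 0.7 to 1.5 per SD of Week 24 worsening.

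- 15.5% missing overall: completers attenuate the effect by 1.7% to 10.5%. Placebo loses 16.6% to 18.5% of subjects, active 12.4% to 14.5%.
- Extending to 23% missing raises the upper end to about 12%, that is 0.12 × 0.5 = 0.06 SD.
- With Week 24 in the model, the estimate stays within 1% of the truth.

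**Boundary cases** (ρ 0.5 to 0.7, true difference 0.5 SD):

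- Same form and same rate of dropout in both arms: bias about zero for both methods. This differs from the case above, where one rule produces unequal rates because placebo is worse at Week 24.
- Dropout driven by Week 24 on placebo, random on active: completer bias 0.06 to 0.09 SD at 10% missing and 0.12 to 0.16 SD at 20%; about zero with Week 24 modelled.
- Placebo dropout driven by the unseen Week 52 value, random on active (10% to 20% missing): completer bias 0.12 to 0.23 SD; 0.07 to 0.18 SD remains with Week 24 modelled.

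**The case against.** A prespecified ANCOVA with only two post-baseline scans by Week 52 is a defensible choice, and the gain from a repeated-measures model at 10% missing is small. That stands, and it keeps this a minor point. It does not explain why QLF differs from the three endpoints above it.

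A reader might also infer more than the documents support:

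- **That the plan excludes subjects without a Week 52 scan.** It does not say so. That is how ANCOVA behaves by default. This protocol itself pairs a ranked ANCOVA with imputation for FVC% predicted, and the Study SAP may hold a rule for QLF.
- **That every subject has a Week 24 scan.** It is scheduled for all. A subject who leaves before Week 24 has at most an early-termination scan.
- **That the ANCOVA assumes away informative dropout and the mixed model would cure it.** The mixed model assumes MAR and leaves bias when dropout follows unseen Week 52 values. The tipping-point analysis in 8.5.2 refers to the efficacy results generally but sits under the primary endpoint, so its reach to QLF is unclear.
- **That fibrosis worsening on HRCT drives subjects out.** No source says this. The ILD progression criteria use FVC and DLCO, and subjects who stop IMP are still expected at Week 52. The link is plausible, not documented.

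**Conclusion.** The point holds in a limited form. As written, QLF has a weaker analysis than its neighbours in the same hierarchy: one visit, no visible missing-data rule, and an intermediate scan left unused. With ρ of 0.6 to 0.8 and Week 24 available in all, modelling that scan makes the SE about 2% to 3% smaller at 10% missing. If dropout rises with Week 24 worsening under a common rule, completers attenuate the effect by roughly 2% to 12% at 15% to 23% missing; if form and rate match across arms, there is essentially no bias. All these sizes rest on assumed QLF effect, correlation and dropout.

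The larger open question is the conflict between 8.5.2 and 8.5.3 on off-treatment data, because it decides how many Week 52 scans are usable.

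None of this should be read as a fault in the abbreviated report. The addendum (sections 5, 11 and 16) drops the full preplanned analyses, imputes no missing efficacy data, and gives QLF summary statistics without tests or confidence intervals. The point applies to the design as written and to any reuse of it.

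**What to change.** Amend Protocol 8.5.3 item 4 and the Study SAP together:

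1. Analyse QLF change at Weeks 24 and 52 with a repeated-measures model: treatment, visit, treatment-by-visit, baseline QLF, baseline QLF-by-visit, and the two covariates already named (baseline FVC% predicted and duration of prior mycophenolate use). Test the Week 52 treatment contrast.
2. Use an unstructured within-subject covariance and no added random intercept. With two visits, the unstructured matrix already has three parameters (two variances and one covariance), which is all the data can identify; a random-intercept variance would be a fourth.
3. State explicitly that the tipping-point analysis in 8.5.2 also covers QLF, since the model above handles only dropout explained by the Week 24 scan.
4. Reconcile 8.5.2 and 8.5.3 on whether scans taken after stopping IMP are included.

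The cost is wording in both documents, not the SAP alone. No visit or scan is added, because the Week 24 HRCT is already in the schedule, and the Week 52 target is unchanged.

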8.6 Interim and Additional Planned Analyses

The interim futility analysis on the primary endpoint will be performed by an independent third party statistician when approximately 88 subjects have either completed 52 weeks of treatment or prematurely discontinued from the trial. The results of interim analysis will be reviewed confidentially by IDMC. The futility boundary is non-binding (to be specified in the IDMC charter). Additional analysis of the primary and secondary endpoints is allowed at the IDMC's discretion and supported by the independent third-party statistician. Based on the totality of the information at interim, the IDMC will make a recommendation to the Sponsor on continuing or stopping the trial for futility. There is no prespecified boundary for efficacy, therefore there is no alpha spending for the interim analysis.

The primary analysis will be performed by the Sponsor/Contract Research Organization staff when all subjects have either completed 52 weeks of treatment or prematurely discontinued from the trial. Results will be generated on the aggregate group level and reviewed by a restricted group to limit initial dissemination. The access of individual treatment information will be controlled to not impact the trial conduct.

The sites and subjects remain blinded until the end of the trial. The trial will continue as planned and a final treatment analysis will be performed when all subjects have either completed 104 weeks of treatment or prematurely discontinued from the trial.

The final database will be locked after all subjects have completed the 12 weeks of safety follow-up or prematurely discontinued from the trial. A final follow-up analysis will be performed after the final database lock.

9 Ethical and Regulatory Aspects

9.1 Responsibilities of the Investigator

The Investigator is responsible for the conduct of the trial at the site and will ensure that the trial is performed in accordance with this protocol, the ethical principles outlined in the Declaration of Helsinki, ICH GCP, and any other applicable regulations. The Investigator must ensure that only subjects who have given informed consent are included in the trial.

According to United States Code of Federal Regulations Part 54.2 (e), for trials conducted in any country that could result in a product submission to the United States Food and Drug Administration (FDA) for marketing approval and could contribute significantly to the demonstration of efficacy and safety of an IMP (which are considered "covered clinical trials" by the FDA), the Investigator and all subinvestigators are obliged to disclose any financial interest which they, their spouses, or their dependent children may have in the Sponsor or the Sponsor's product under study. This information is required during the trial and for 12 months following completion of the trial.

9.2 Subject Information and Informed Consent

An unconditional prerequisite for each subject prior to participation in the trial is written informed consent, which must be given before any trial-related activities are carried out. Adequate information must therefore be given to the subject by the Investigator or an appropriate designee (if local regulations permit) before informed consent is obtained.

A subject information sheet must be prepared in the local language in accordance with ICH GCP and will be provided by the Sponsor for the purpose of obtaining informed consent. In addition to providing this written information to a potential subject, the Investigator or a designee will inform the subject verbally of all pertinent aspects of the trial, using language chosen so that the information can be fully and readily understood by laypersons. The subject will be given sufficient time to read the information and the opportunity to ask questions and to request additional information and clarification.

If permitted by national regulations, a person other than the Investigator may inform the subject about the trial and sign the Informed Consent Form, as above.

After the information is provided by the Investigator, the Informed Consent Form must be signed and dated by the subject and the Investigator.

The signed and dated declaration of informed consent will remain at the Investigator's site, and must be safely archived so that the forms can be retrieved at any time for monitoring, auditing, and inspection purposes. A copy of the signed and dated information and Informed Consent Form should be provided to the subject prior to participation.

Whenever important new information becomes available that may be relevant to informed consent, the Investigator will revise the subject information sheet and any other written information to be provided to the subjects and submit them to the IRB for review and opinion. Using the approved revised subject information sheet and other written information, the Investigator will explain the changes to the previous version to each trial subject and obtain new written consent for continued participation in the trial. The subject will be given sufficient time to read the information and the opportunity to ask questions and to request additional information and clarification about the changes.

Rich Pharmacokinetic Sampling Informed Consent

All subjects who are enrolled in the trial will be eligible to participate in the optional rich PK analysis. As participation is optional, the subjects willing to participate will need to sign a specific PK Informed Consent Form.

CCI [REDACTED]

[REDACTED]

CCI

9.3 Subject Identification and Privacy

A unique number will be assigned to each subject, immediately after informed consent has been obtained. This number will serve as the subject's identifier in the trial as well as in the clinical trial database. All subject data collected in the trial will be stored under the appropriate subject number. Only the Investigator will be able to link trial data to an individual subject via an identification list kept at the site. For each subject, original medical data will be accessible for the purposes of source data verification by the Monitor, audits, and regulatory inspections, but subject confidentiality will be strictly maintained.

Data protection and privacy regulations will be observed in capturing, forwarding, processing, and storing subject data. Subjects will be informed accordingly, and will be requested to give their consent on data handling procedures in accordance with national regulations.

Storage and analyses of samples will be handled according to the specifications as described in the Informed Consent Form.

